6.4.8.3. Diabetes Assessment

Diabetes will be assessed by the analysis of:

- TEAEs
- change in glucose-related laboratory values over time
- shifts from baseline in glucose control category and,
- incidence of post-baseline new onset of diabetes.

Note that diabetes related tables dealing with the fasting glucose parameter will require the lab sample to be taken while fasting. Samples taken while the subject was not fasting will not be analyzed.

6.4.8.3.1. Diabetes TEAE

New onset/worsening of diabetes will be identified using SMQ and AE terms (refer to Appendix 5 on Standardized MedDRA Queries (SMQ) and AE terms). The analysis will be performed for all subjects and then by baseline diabetes status. A subject will be identified as being diabetic at baseline if the targeted medical history notes that the subject is diabetic or the baseline HbA1c value is $\geq 6.5\%$.

6.4.8.3.2. Change in Glucose-related Laboratory Values Over Time

This analysis only utilizes laboratory data (fasting glucose and HbA1c). The change from baseline to the last on-treatment observation and the worst on-treatment observation will be summarized separately for fasting glucose and HbA1c overall and then by baseline glucose control status. Baseline glucose control status will be identified separately for fasting glucose and HbA1c using the values provided in the table below (note that medical history will not be taken into account for this analysis). Figures will also be created showing mean fasting glucose and HbA1c values over time by baseline glucose control status.

Parameter	Baseline Glucose Control Status	Baseline Laboratory Values*
Fasting Glucose	Normal	<100 mg/dL
	Impaired	≥100 to <126 mg/dL
	Diabetes	≥126 mg/dL
HbA1c	Normal	<5.7%
	Impaired	≥5.7 to <6.5%
	Diabetes	≥6.5%

^{*}Using average of Screening and Day 1 fasting glucose values. If one fasting glucose value is missing (Screening or Day 1), the assessment will be based on the available data.

6.4.8.3.3. Shifts from Baseline in Glucose Control Category

Shifts from baseline in glucose control category will be summarized two different ways. The change from baseline to the worst-on-treatment and then again for the last-on-treatment laboratory values will be used to classify the on-treatment glucose control category. Note that medical history will not be taken into account for this analysis. If consecutive fasting glucose measurements fall in two separate categories, or if only one pre- or post-baseline fasting glucose measurement is available, then the classification will be based on the HbA1c measurements only. If HbA1c is missing then both consecutive fasting glucose measurements must fall in a category otherwise the lower category will be used.

Shift Category*	Baseline Values**	Post-baseline Values
Normal to Normal (no change)	Fasting glucose <100 mg/dL on Screening or Day 1	Fasting glucose <100 mg/dL on two consecutive occasions
	AND	AND
	HbA1c <5.7%	HbA1c <5.7%
Normal to Impaired	Fasting glucose <100 mg/dL on Screening or Day 1 AND HbA1c <5.7%	Fasting glucose ≥100 and <126 mg/dL on two consecutive occasions OR HbA1c ≥5.7 and <6.5%
Normal to Diabetes	Fasting glucose <100 mg/dL on Screening or Day 1 AND	Fasting glucose ≥126 mg/dL on two consecutive occasions OR

	HbA1c <5.7%	HbA1c ≥6.5%
Impaired to Normal	Fasting glucose ≥100 and <126 mg/dL on Screening and Day 1 OR HbA1c ≥5.7 and <6.5%	Fasting glucose <100 mg/dL on two consecutive occasions AND HbA1c <5.7%
Impaired to Impaired (no change)	Fasting glucose ≥100 and <126 mg/dL on Screening and Day 1 OR HbA1c ≥5.7 and <6.5%	Fasting glucose ≥100 and <126 mg/dL on two consecutive occasions OR HbA1c ≥5.7 and <6.5%
Impaired to Diabetes	Fasting glucose ≥100 and <126 mg/dL on Screening and Day 1 OR HbA1c ≥5.7 and <6.5%	Fasting glucose ≥126 mg/dL on two consecutive occasions OR HbA1c ≥6.5%
Diabetes to Normal	Fasting glucose ≥126 mg/dL on Screening and Day 1 OR HbA1c ≥6.5%	Fasting glucose <100 mg/dL on two consecutive occasions AND HbA1c <5.7%
Diabetes to Impaired	Fasting glucose ≥126 mg/dL on Screening and Day 1 OR HbA1c ≥6.5%	Fasting glucose ≥100 and <126 mg/dL on two consecutive occasions OR HbA1c ≥5.7 and <6.5%
Diabetes to Diabetes (no change)	Fasting glucose ≥126 mg/dL on Screening and Day 1 OR HbA1c ≥6.5%	Fasting glucose ≥126 mg/dL on two consecutive occasions OR HbA1c ≥6.5%

^{*}No change (Normal to Normal, Impaired to Impaired, and Diabetes to Diabetes), Worsened (Normal to Impaired, Normal to Diabetes, and Impaired to Diabetes), and Improved (Impaired to Normal, Diabetes to Impaired, and Diabetes to Normal) categories will also be summarized.

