6.4.8.3.4. Incidence of Post-baseline New-Onset of Diabetes

The number of subjects who shift from no diabetes at baseline (defined as no medical history of diabetes in the targeted medical history CRF, HbA1c <6.5% at baseline, and fasting glucose <126 mg/dL at baseline (note that baseline is defined as the average of Screening and Day 1 fasting glucose values, if one fasting glucose value is missing (Screening or Day 1), the

^{**} If one fasting glucose value is missing (Screening or Day 1), the assessment will be based on the available data.

assessment will be based on the available data) to diabetes will be summarized. A 4-component definition of diabetes will be utilized. The 4 components are provided below.

- 1. Diabetic TEAEs identified by the SMQ search (see Appendix 5), or
- 2. Post-baseline fasting glucose ≥126 mg/dL on two consecutive occasions, or
- 3. Initiation of anti-diabetic medication at any time post-baseline, or
- 4. At least one post-baseline Hba1c \geq 6.5%.

The number of subjects who have any of the 4 components will be summarized (post-baseline new-onset of diabetes) along with each component. This analysis will be performed for those subjects who have fasting glucose at baseline < 100 mg/dL and then for those with fasting glucose at baseline $\ge 100 \text{ and} < 126 \text{ mg/dl}$ (normoglycemic).

The time to new-onset diabetes will also be summarized. Only subjects without diabetes at baseline will be included in the analysis. The time (weeks) to new-onset diabetes will be calculated from the date of the first administration of study drug.

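### With HbA1c below 5.7%, the glucose shift table's tie rule classes one impaired plus one diabetic fasting glucose as Normal, so rising glucose can be counted as Improved

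*SAP*

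**What the plan says.** SAP 6.4.8.3.3 plans a shift table from baseline to the worst, and separately to the last, on-treatment glucose category.

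- **Normal (post-baseline):** "Fasting glucose <100 mg/dL on two consecutive occasions AND HbA1c <5.7" (HbA1c in percent).
- **Impaired (baseline):** "Fasting glucose ≥100 and <126 mg/dL on Screening and Day 1 OR HbA1c ≥5.7 and <6.5". The OR means that glucose alone can make a subject Impaired.
- **Diabetes (post-baseline):** "Fasting glucose ≥126 mg/dL on two consecutive occasions OR HbA1c ≥6.5".

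The text above the table adds a tie rule. Its trigger is "If consecutive fasting glucose measurements fall in two separate categories, or if only one pre- or post-baseline fasting glucose measurement is available", and its consequence is "then the classification will be based on the HbA1c measurements only". There is also a fallback: "If HbA1c is missing then both consecutive fasting glucose measurements must fall in a category otherwise the lower category will be used".

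The footnotes group the shifts. One group is "Improved (Impaired to Normal, Diabetes to Impaired, and Diabetes to Normal) categories will also be summarized". Footnote ** deals with a single baseline glucose: "If one fasting glucose value is missing (Screening or Day 1), the assessment will be based on the available data".

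**The concern.** Using HbA1c to settle a tie is reasonable when one glucose is normal and the other is not. The same sentence also covers a pair in which both values are abnormal, one impaired and one diabetic. There the disagreement concerns only how abnormal the glucose is, yet a normal HbA1c moves the subject all the way to Normal.

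This is a planned safety table for glucose worsening. Subjects close to the 126 mg/dL boundary are the most likely to have such a pair, and for some of them the table would report the direction of change wrongly.

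A second, smaller matter is that the text and footnote ** can be read differently for a subject with only one baseline glucose.

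**Working it through.** **Inputs.** Category limits, tie rule, missing-HbA1c fallback and the Improved grouping are from SAP 6.4.8.3.3. The visit schedule is from SAP 3.8.8.3. The documents give no figure to reproduce. One assumption is needed: where a subject meets two rows of the table, the higher category applies.

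**Step 1: apply the rule to every discordant pair.**

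| Glucose pair | HbA1c <5.7% | 5.7 to <6.5% | ≥6.5% | missing |
|---|---|---|---|---|
| normal + impaired | Normal | Impaired | Diabetes | Normal |
| normal + diabetic | Normal | Impaired | Diabetes | Normal |
| impaired + diabetic | **Normal** | Impaired | Diabetes | Impaired |

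The bold cell is the anomaly, in 1 of the 4 HbA1c states for that pair.

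**Step 2: compare it with its neighbours.**

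- 110/112 mg/dL, HbA1c 5.6%: concordant, so the OR gives Impaired.
- 118/130 mg/dL, HbA1c 5.6%: discordant, so HbA1c alone gives Normal, although both glucose values are higher.
- 118/130 mg/dL, HbA1c missing: the fallback gives Impaired.

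**Step 3: shifts, HbA1c 5.6% throughout.**

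- 105/108 to 120/135 mg/dL: Impaired to Normal, counted as Improved while glucose rose.
- 118/130 to 110/112 mg/dL: Normal to Impaired, counted as Worsened while glucose fell.

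**Step 4: how many patterns are affected.** There are 6 possible category pairs at each time. In 14 baseline-to-later combinations at least one value rises a category and none falls; with 4 HbA1c states held constant, 14 × 4 = 56. One of the 56 is reported as Improved: two impaired values, then impaired + diabetic, HbA1c <5.7%. Its mirror image is the only one of the 56 falling patterns reported as Worsened.

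**Step 5: how often a pair could be discordant (illustration on assumed values).** Take normal within-subject variation around a usual level. Let p = P(99.5 to 125.5 mg/dL) and q = P(above 125.5). The chance that one pair is impaired + diabetic is 2pq.

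| Usual level | 2pq, SD 6 / 8 / 10 |
|---|---|
| 120 | 0.29 / 0.37 / 0.40 |
| 124 | 0.48 / 0.49 / 0.49 |
| 126 | 0.50 / 0.50 / 0.50 |

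A false Improved also needs two impaired values at baseline, so with stable glucose its chance is p² × 2pq. At SD 8:

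- level 120: 0.749² × 0.368 = 0.21
- level 124: 0.573² × 0.488 = 0.16
- level 126: 0.475² × 0.498 = 0.11

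All three apply before requiring HbA1c <5.7%. The false Worsened has the same probability.

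**Step 6: the worst-on-treatment version.** Fasting glucose is drawn at seven post-baseline visits (Days 90, 150, 270, 330, 450, 510, 540). Suppose that worst means the worst category over consecutive pairs, which the SAP does not state. Under the Step 5 assumptions with complete visits, the chance that no two consecutive values share an abnormal category is only 0.3% to 1.7%. A concordant pair would then nearly always set the class at Impaired or above.

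**Step 7: test the remedy.** Use the lower glucose category, then the worse of that and HbA1c. In the Step 1 table only the bold cell changes, from Normal to Impaired. None of the 56 rising patterns is then reported as Improved.

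**The case against.** **The tie-breaker is a prespecified choice.** It settles pairs that the table does not cover. A post-baseline 95/110 pair also fails the Normal row, yet HbA1c is accepted as arbiter there. This stands: failing that row is not in itself the error. The error is the ordering shown in Step 2, which the objection does not answer.

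**The glucose signal appears elsewhere.** SAP 6.4.8.2 has laboratory shifts on worst values. SAP 6.4.8.3.2 summarises fasting glucose separately from HbA1c. SAP 6.4.8.3.1 covers diabetes adverse events, and SAP 6.4.8.3.4 has a four-component new-onset definition that does not use the tie rule. This stands and limits the reach.

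**Stronger readings that the documents do not support.**

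- A reader might infer that every impaired/diabetic pair is classed Normal. That holds only with HbA1c <5.7%.
- A reader might take 0.37 to 0.50 (SD 8) as the rate of false improvement. It is the chance of one discordant pair under assumed values.
- A reader might infer that the table is tilted towards apparent safety. The rule is the same in both arms, and with stable glucose the two errors are equally likely.
- A reader might say that a lone baseline 140 mg/dL with HbA1c 5.6% is Normal by the text and Diabetes by footnote **. The footnote covers baseline only and refers to available data, which could include HbA1c, and the baseline Diabetes row asks for both Screening and Day 1. This is an ambiguity to resolve; the Diabetes result is an inference.

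**A rewrite now is post hoc.** The SAP Addendum (section 1) places its changes after lock and unblinding. This stands and governs how a correction should be shown.

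**Conclusion.** The concern holds in a narrow form. For an impaired + diabetic glucose pair with HbA1c <5.7%, the stated rule gives Normal, out of order with a lower concordant pair and with the SAP's own result when HbA1c is missing. It can misreport direction both ways.

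The reach is this one descriptive table, chiefly its last-on-treatment version. No primary, key secondary or new-onset diabetes result is affected. The number of affected subjects among the 482 enrolled is not given, and the probabilities above rest on assumed glucose levels and SDs. The pattern count assumes that the higher category applies when two rows are met; the limit to the last-on-treatment version depends on what worst means.

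It is worth correcting because a safety table should not count rising glucose as Improved when a small rewording prevents it.

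**What to change.** In SAP 6.4.8.3.3, replace the tie rule for discordant pairs with wording such as: when two consecutive fasting glucose values fall in different categories, the glucose component is the lower of the two, and the subject's category is the worse of the glucose component and HbA1c. This extends the SAP's existing missing-HbA1c rule, and 95/110 mg/dL with HbA1c <5.7% stays Normal.

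Reconcile the text and footnote ** so that one rule applies to a single baseline glucose.

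In the same edit, state which pair defines worst-on-treatment. State also which HbA1c applies to pairs that include Day 150, 330 or 510, when SAP 3.8.8.3 schedules none.

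Present the corrected table beside the original, labelled as a post-lock change. Addendum section 2.3 already does this for Hy's Law by adding a second summary.

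Cost: a few sentences, a small program change and one extra table; no new data. The downside is that a few more subjects may be shown as Impaired.

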6.4.8.3.4. Incidence of Post-baseline New-Onset of Diabetes

The number of subjects who shift from no diabetes at baseline (defined as no medical history of diabetes in the targeted medical history CRF, HbA1c <6.5% at baseline, and fasting glucose <126 mg/dL at baseline (note that baseline is defined as the average of Screening and Day 1 fasting glucose values, if one fasting glucose value is missing (Screening or Day 1), the

^{**} If one fasting glucose value is missing (Screening or Day 1), the assessment will be based on the available data.

assessment will be based on the available data) to diabetes will be summarized. A 4-component definition of diabetes will be utilized. The 4 components are provided below.

- 1. Diabetic TEAEs identified by the SMQ search (see Appendix 5), or
- 2. Post-baseline fasting glucose ≥126 mg/dL on two consecutive occasions, or
- 3. Initiation of anti-diabetic medication at any time post-baseline, or
- 4. At least one post-baseline Hba1c \geq 6.5%.

The number of subjects who have any of the 4 components will be summarized (post-baseline new-onset of diabetes) along with each component. This analysis will be performed for those subjects who have fasting glucose at baseline < 100 mg/dL and then for those with fasting glucose at baseline $\ge 100 \text{ and} < 126 \text{ mg/dl}$ (normoglycemic).

The time to new-onset diabetes will also be summarized. Only subjects without diabetes at baseline will be included in the analysis. The time (weeks) to new-onset diabetes will be calculated from the date of the first administration of study drug.

6.4.8.4. Anti-Drug Antibody

ADA is being assessed and will be listed in a separate ADA report. If there are ADA findings, further characterization and additional evaluations may be performed on safety and efficacy parameters.

6.4.8.5. Vital Signs

Observed value, change, and percent change from Day 1 in vital signs will be summarized descriptively at each scheduled time point by treatment group.

The change from baseline to EOS will also be summarized by the following categories:

- Systolic blood pressure (mmHg):
 - o ≤ -20
 - \circ > -20 to \leq -10
 - \circ > -10 to < -5
 - \circ > -5 to < 5
 - \circ > 5 to < 10
 - $\circ \geq 10 \text{ to} \leq 20$
 - $\circ \geq 20$
- Diastolic blood pressure (mmHg):
 - ≤-10
 - \circ > -10 to \leq -5
 - \circ > -5 to < -3
 - \circ > -3 to < 3

- $\circ \geq 3 \text{ to} \leq 5$
- $\circ \geq 5 \text{ to} \leq 10$
- ≥10

6.4.8.6. Electrocardiograms

The percentage of subjects with abnormal ECG findings reported as AEs will be summarized by treatment group within the overall assessment of cardiac safety.

6.4.8.7. Neurological Examinations

The percentage of subjects with a treatment-emergent abnormal neurological event and the specific abnormality reported as adverse events, will be summarized by treatment group.

7. **COMPUTER METHODS**

Statistical analyses will be performed using SAS (version 9.4 or later version).

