3.4. Secondary Endpoints

The key secondary endpoints of this study are:

- Absolute change in LDL-C from baseline to Day 510
- Time adjusted absolute change in LDL-C from baseline after Day 90 and up to Day 540
- Percentage change from baseline to Day 510 in PCSK9, total cholesterol, ApoB, and non-HDL-C

The other secondary endpoints of this study are:

- Mean maximum percentage change in LDL-C
- Absolute change from baseline to Day 510 in PCSK9, total cholesterol, ApoB and non-HDL-C
- Absolute change and percentage change in LDL-C from baseline to each assessment time up to Day 540
- Individual responsiveness defined as the number of subjects reaching on treatment LDL-C levels of <25 mg/dL, <50 mg/dL, <70 mg/dL, and <100 mg/dL at Day 510
- Proportion of subjects in each group with greater or equal to 50% LDL-C reduction from baseline
- Absolute change and percentage change in other lipids, lipoproteins, apolipoproteins, and PCSK9 from baseline at each subsequent visit to Day 540
- Proportion of subjects in each group who attain global lipid targets for their level of ASCVD risk
- Safety and tolerability profile of inclisiran as measured by AEs, SAEs, vital signs, clinical laboratory values, ECG measurements and formation of ADA and subsequent characterization of ADA

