8.3.2. Other safety related information

Injection site reactions (ISR) including individual signs or symptoms at the injection site following investigational product administration should be recorded on specifically designed eCRF pages. Photographs of ISR, if they were obtained during the study visits, should be forwarded to study inbox.

Other safety related information that should be reported as adverse events in accordance with the process described in section 8.4 include:

- Abnormal neurological examination, eg, peripheral sensory and motor evaluation, an assessment of gait, pain, position, strength and reflexes ([APPENDIX D](#)).
- Potential anaphylactic reactions assessed by Sampson criteria ([APPENDIX E](#)). If Sampson criteria are positive, confirm by elevation of tryptase in blood plasma measured within 30 minutes of symptoms.
- Hyperglycemia-related AEs:
 - Report ‘New onset of diabetes’ in subjects with no medical history of diabetes when:
 - HbA1C becomes $\geq 6.5\%$ and/or
 - Two consecutive values of fasting plasma glucose that are ≥ 126 mg/dL
 - If a new concomitant medication for control of plasma glucose is added, further information to assess for a diagnosis of new onset diabetes will be collected.

Report ‘Worsening of the glycemic control’ or ‘diabetic complications’ in subjects with a medical history of disease (HbA1C $\geq 6.5\%$ at baseline) when:

- HbA1C increases from baseline $> 0.5\%$ and/or
- New concomitant medication or increase in dose of current antidiabetic therapy is initiated to improve the control of plasma glucose level.

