10.4.4.4. Neurological Examinations

The percentage of subjects with a treatment-emergent abnormal neurological examination and the specific abnormality reported will be summarized by treatment group.

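### SAP 6.4.8.7 swaps the protocol's neurological-examination rate for a count of AEs without declaring it; separately, the ECG measurements in the safety endpoint get no summary of their own

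*SAP*

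**What the plan says.** **Neurological examination.** Protocol 10.4.4.4: "The percentage of subjects with a treatment-emergent abnormal neurological examination and the specific abnormality reported will be summarized by treatment group". SAP 6.4.8.7 keeps the same heading but summarises "The percentage of subjects with a treatment-emergent abnormal neurological event and the specific abnormality reported as adverse events". Both schedules of assessments place the examination on Day 1 and at EOS (Day 540) and nowhere else. Protocol 8.3.2 introduces a list with "Other safety related information that should be reported as adverse events in accordance with the process described in section 8.4 include", and the list contains "Abnormal neurological examination, eg, peripheral sensory and motor evaluation, an assessment of gait, pain, position, strength and reflexes". SAP 4.5.2 repeats this.

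**ECG.** Protocol 3.4 includes among the secondary endpoints "Safety and tolerability profile of inclisiran as measured by AEs, SAEs, vital signs, clinical laboratory values, ECG measurements". The schedule has 12-lead ECGs at screening, Day 1 and EOS. Protocol 10.4.4 has no ECG subsection. SAP 6.4.8.6 says "The percentage of subjects with abnormal ECG findings reported as AEs will be summarized by treatment group within the overall assessment of cardiac safety". SAP 3.8.6 passes only changes judged significant into the AE data and does not define significant.

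**The concern.** An examination result and an AE report are different measurements. The examination is a scheduled assessment in both arms, before the first dose and at the end, so each subject examined twice contributes a before-and-after result, and a subject not re-examined is visibly missing. An AE report exists only if someone files it, can arise from a complaint at any time, and leaves no trace of whether an examination took place. If the AE count stands in for the examination, the reader of the study report cannot recover the rate of new abnormality among those examined, which is what the protocol said would be shown. For ECG, a named component of the secondary safety endpoint reaches the tables only through an investigator judgement for which no criterion is given.

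**Working it through.** No figure in the plan bears on this, so the check is mainly a comparison of texts.

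1. **Was the neurological analysis changed?** Yes. The protocol's unit is an examination that became abnormal; the SAP's unit is an event reported as an AE.

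2. **Was the change declared?** No. SAP section 8 lists seven changes, down to the renaming of one endpoint, and this is not among them. The SAP Addendum (2.1 to 2.5) does not mention it either.

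3. **Is the examination tabulated elsewhere?** No other SAP section does so. The neurological items in SAP 6.4.8.1 and Appendix 5 are searches of AE terms. The general clause in SAP 6.3.1 covers all collected data but can be met by listings alone.

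4. **Would the AE percentage equal the protocol's rate?** Write *p* for the rate of new abnormality among re-examined subjects, *c* for the share of those abnormalities reported as AEs, *u* for the share of treated subjects never re-examined, and *s* for the share of treated subjects counted only through neurological AEs that did not come from the examination. Over all treated subjects:

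   AE percentage = (1 − *u*) × *p* × *c* + *s*

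   - *c*: Protocol 8.3.2 aims at *c* = 1. The documents give no observed value.
   - *u*: SAP 6.4.8.7 states no denominator. The safety population is everyone dosed, and a subject without an AE report looks the same whether examined and normal or not re-examined. As an illustration, assume that the planned dropout of about 5% means 5% without an EOS examination: 482 × 0.95 = 457.9, about 458 examined. With *c* = 1, *s* = 0 and an assumed *p* of 4.0%, the AE percentage is 0.95 × 4.0% = 3.8%. For *u* between 0 and 5% it lies between 4.0% and 3.8%, so this part is small.
   - *s*: unknown. It pushes the percentage up, and an AE-only table cannot separate it from examination findings.

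5. **Timing.** SAP 6.4.8.1 counts an AE as treatment-emergent if it occurs in the treatment period. SAP 2.4 runs that period from Day 1 to Day 510 and lists EOS as a separate period. The EOS visit window is ±14 days, so the earliest on-schedule EOS visit is Day 540 − 14 = Day 526, after Day 510. Read literally, an abnormality first found in a completer at EOS is not treatment-emergent. One found in an early discontinuer whose EOS visit was brought forward to before Day 510 would be.

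6. **ECG.** Protocol 10.4.4 specifies no ECG analysis, so SAP 6.4.8.6 displaces nothing. But the other measured components of the same endpoint are summarised from their values: vital signs in SAP 6.4.8.5, and laboratory tests, with shift tables, in 6.4.8.2. ECG is not. The AE route is also weaker here, because ECG is not on the Protocol 8.3.2 list and Protocol 7.1.6 gives no instruction to report changes as AEs.

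**The case against.** The best defence is that the AE route for neurology is the protocol's own. If sites follow Protocol 8.3.2, every abnormal examination produces an AE, and the SAP table then shows what the examination found. Nothing in the documents points to under-reporting. That stands, and it is why no loss can be asserted. It does not supply a denominator or separate examination findings from symptoms.

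Second, the timing point proves too much: on the same literal reading, the protocol's own examination rate would be empty for completers, since their only scheduled post-baseline examination is at Day 540. AEs are collected through EOS (Protocol 8.4.2), and the observational period in Protocol 10.3.3 includes the EOS visit, so the sponsor probably means to count EOS findings. That is a fair reading, but the SAP does not say so, and one sentence would settle it.

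Third, subjects who stop early and decline further visits are to have EOS procedures as soon as possible, which keeps the number never re-examined low. Neurological safety is also covered by the Appendix 5 searches. Both are true; the second shows that AE-based neurological information is already produced elsewhere, so the examination is what 6.4.8.7 could add.

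Fourth, the eCRF is not among the documents, and Protocol Appendix D is a recommended examination without an overall normal/abnormal grade. Whether a codable result exists is unconfirmed, and the fix has to allow for that.

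**Conclusion.** The point holds in a limited form. For the neurological examination, a protocol-specified descriptive safety result was replaced by a different one and the change was not declared. The practical loss may be small and cannot be quantified: it depends on how completely abnormal examinations become AEs, how many neurological AEs arise outside the examination, and whether EOS findings count as treatment-emergent. The only part that can be illustrated, the denominator, moves an assumed 4.0% to 3.8%. For ECG, the gap is an endpoint component without a measurement-based summary.

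A reader might infer three stronger things that the documents do not support. One is that the SAP also replaced a promised ECG analysis; the protocol promised no ECG rate, so section 8 had no ECG change to list. Another is that findings not reported as AEs are lost from the trial; SAP 6.3.1 commits to summarising or listing all collected data, so they may appear in listings though not in a table. The third is that the trial's ability to detect a neurological difference falls by a stated amount; the SAP plans no test of these percentages, and any such figure would rest on invented event and capture rates.

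**What to change.** - **SAP 6.4.8.7:** restore a Day 1 to EOS summary of the examination by arm, normal or abnormal with the specific abnormality as recorded. Use subjects with both examinations as the denominator and show the number not re-examined. State that EOS findings count as treatment-emergent.
- **SAP 6.4.8.6:** add a baseline-to-EOS summary of the recorded ECG result by arm.
- **Both sections:** keep the AE summaries alongside.
- **SAP section 8:** list the neurological change. If the sponsor prefers AE reports alone, section 8 should say so, and the SAP still needs the rule on Day 540 findings.

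The cost is two descriptive tables from assessments already scheduled, with no effect on alpha or on any efficacy analysis. Both depend on the eCRF holding a codable result, which should be checked first.
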